Participants will be seen weekly throughout the 12-week experimental period. Study Weeks 2, 6, and 12 will take approximately 2-4 hours each. All other sessions will last 1-2 hours. As a part of each experimental visit, participants will be asked to come to UHC for a product exchange. All participants must pass a COVID19 screening before entering the building. Participants will be instructed to contact the RA at the office when they get to the clinic to ensure that there is enough space in the smoking chambers to house all participants while abiding by safety guidelines as detailed on page 14 of the protocol. When invited into the lab, the participant will be shown to a smoking chamber and will be instructed to place their bag of product outside of the chamber. The participant will wait here while the RA processes and returns product through the randomization database. Then the RA will dispense new product and bring the bag back to the participant's smoking chamber and leave it on the ground in front of the chamber. When the RA deems it safe for the participant to exit the chamber, the RA will instruct the participant that they can leave. The RA will instruct the participant to observe social distancing measures during this exchange, providing clarification if necessary.

Visit scheduling requirements for experimental period:

The ideal scheduling window between each visit is 7 days based on the date of the Baseline 2 (randomization) Visit. For additional scheduling requirements, refer to the '*Scheduling Visits SOP*'. If a participant misses a visit and is not able to reschedule during the window (\pm 3 days), that visit will not be 'made-up' in the future. All measures that were not completed will be considered missing data and will not be collected during future visits. If a visit mistakenly occurs outside of the designated window, this is a protocol deviation. A 'Non-Medical Event Form' will need to be completed. Additionally, each visit should occur at approximately the same time of day \pm 1 hours.

If a participant is not able to attend her Week 12 visit, then it should be rescheduled even if it is outside of the scheduling window. This will be documented as a protocol deviation.

Experimental Visits: Study Weeks 1, 3, 5, 7, 9, and 11:

Measures/Assessments

Physiological Measures will be collected and entered directly into REDCap by the interviewer:

- 1) CO
- 2) Blood pressure
- 3) Heart rate

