The following assessments will be administered as an interview and will be entered directly into REDCap by the interviewer:

- 1) Concomitant Medications Form
- 2) Time Since Last Cigarette Questionnaire
- 3) Health Changes Questionnaire
- 4) Medical Event Form (if applicable)
- 5) Maintenance Drug Dose Questionnaire (if applicable)

The following assessments will be completed by the participant directly in REDCap:

- 1) BDI
- 2) OASIS
- 3) MNWS
- 4) QSU brief – with reference to assigned cigarette
- 5) CES – with reference to assigned cigarette
- 6) PUQE-24
- 7) COVID-19 Symptom Questionnaire

In the event that the REDCap website is not functioning, the assessments will be administered aloud and participant answers will be recorded securely. The interviewer will enter the data into REDCap when it resumes functioning properly. A note indicating that REDCap was not functioning during the session should be recorded in the 'End of Visit Evaluation Form'.

Experimental Visits: Study Weeks 2, 4, 6, 8, 10 & 12:

Measures/Assessments

Physiological measures will be collected and entered directly into REDCap by interviewer:

- 1) CO
- 2) Blood pressure
- 3) Heart rate

The following assessments will be administered as an interview and will be directly entered into REDCap by the interviewer:

- 1) Concomitant Medications Form
- 2) Time Since Last Cigarette Questionnaire
- 3) Health Changes Questionnaire
- 4) Medical Event Form (if applicable)
- 5) Maintenance Drug Dose Questionnaire (if applicable)

The following assessments will be completed by the participant directly in REDCap:

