- If the participant chooses not to receive the study product, have her contact the lab if she lapses and would like to pick up or be mailed the study product prior to her next visit.

If a Participant is Planning to Quit Smoking, but has not initiated the quit attempt:

- Ask if she has identified a target quit date and, if so, what that target date is
- Provide the participant with the '*Clearing the Air*' manual and local smoking cessation resources
- Provide the participant with the study product as usual. Recommend that on the target date she put the product "away" at home as to avoid unwanted cues to smoke.

Abstinence Assessment Session:

After the week 12 visit, participants will be required to attend one additional visit the following day. Participants will have been encouraged to abstain from smoking leading up to this visit. The abstinence assessment session should be scheduled no less than 18 hours and no more than 30 hours after the Week 12 visit. Abstinence will be verified by CO levels that have decreased by at least 50% from the measure taken during the Week 12 visit. This session will allow us to determine whether the experimental cigarettes have reduced the effects of abstinence on these measures relative to the control conditions. If the participant does NOT meet abstinence criteria, she will only receive \$20 for the visit.

Measures/Assessments

Physiological measures will be collected and entered into REDCap by the interviewer:

- 1) CO
- 2) Blood pressure
- 3) Heart rate

The following assessments will be administered as an interview and will be entered directly into REDCap by the interviewer:

- 1) Concomitant Medications Form
- 2) Health Changes Questionnaire
- 3) Time Since Last Cigarette Questionnaire
- 4) Medical Event Form (if applicable)
- 5) Maintenance Drug Dose Questionnaire (if applicable)

The following assessments will be completed by the participant directly in REDCap:

- 1) BDI
- 2) OASIS
- 3) MNWS
- 4) QSU-brief – with reference to assigned cigarette
- 5) CPT - with reference to assigned cigarette
- 6) CES – Usual Brand Cigarette Version
- 7) COVID-19 Symptom Questionnaire

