## 6. Trial Endpoints

### 6.1. Primary Endpoints

The Primary Aim of the extended exposure study is to compare the effects of cigarettes varying in nicotine yield on smoking rate. The primary endpoint is average CPD during Week 12. Additional measures addressing this aim are breath CO level, urinary cotinine concentration, nicotine dependence (Fagerström Test for Nicotine Dependence, Wisconsin Index of Smoking Dependence Motives) scores, nicotine withdrawal (Minnesota Nicotine Withdrawal Scale, Questionnaire of Smoking Urges), and the Cigarette Purchase Task (CPT).

- CPD will be collected by daily Interactive Voice Response (IVR) to assess cigarette use in the days since the last interview. This will yield a continuous record of cigarette use throughout the study. A weekly average will be obtained for analysis by averaging the daily CPD reports.
- Breath CO
  - Collected at baseline and weekly for the duration of the study
- Urinary cotinine concentration
  - Collected at the second baseline, Weeks 6 and 12
- Nicotine dependence and withdrawal
  - Collected at screening, the first baseline, every other week (even weeks for nicotine dependence, odd weeks for nicotine withdrawal) until study completion and the abstinence visit
- CPT
  - Collected at the second baseline and Weeks 2, 6, 12 and the abstinence visit for usual brand cigarette
  - Collected at Weeks 2, 6, and 12 and the abstinence visit for study cigarette
  - Breakpoint: the lowest price at which cigarette consumption is 0.
  - Elasticity of demand: the sensitivity of cigarette consumption to price increases.
  - Omax: the maximum daily expenditure for cigarettes.
  - Pmax: the price at which cigarette expenditure is maximized.
  - Intensity: cigarette consumption at the lowest price (\$0 cost).

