## **7.3. Primary Endpoint Analysis**

### **7.3.1. Primary Analysis**

The primary endpoint is CPD during Week 12, compared to the CPD at baseline. While the primary outcome is the mean total CPD, consisting of both study and non-study cigarettes, the analyses will be repeated examining only the CPD contributed by study cigarettes. CPD will be computed as the mean CPD calculated on a weekly basis. Data analysis will use repeated measures analysis of variance, with two conditions and two time points (baseline and Week 12). In addition, the analysis model will include a random effect for site, a random

participant effect and random error (within-subject error). Variance parameters will be estimated using restricted maximum likelihood method with the Satterthwaite approximation.

Because CPD will be measured weekly, additional analyses will be performed including data collected at all time points. The analysis will be conducted in a manner similar to that described above, with the exception that there will be 13 time points: baseline and Weeks 1 through 12. For these analyses, the variance-covariance structure will be specified as first-order autoregressive.

Additional outcomes include the CPT, breath CO level, urinary cotinine concentration, and nicotine dependence and withdrawal scores. These will be examined in a manner similar to that described above for CPD. Natural log transformations will be performed as needed so that ANOVA model assumptions of normality and equal variances hold. Geometric means in original units will be calculated as well. Note that not all outcomes are assessed at weekly in-person visits. The time points at which each outcome is assessed is described in Section 6.

Finally, several assessments will be made at baseline as well as at the abstinence visit, which occurs the day following the Week 12 assessment. At this visit, measures of craving and withdrawal will be completed. The analysis will be similar to that described above for the CPD comparing baseline CPD to that reported at the end of the trial. The analysis will deviate from that described only in the timing of the tasks, with the time points consisting of the baseline and the abstinence visits, rather than the baseline and Week 12 visits reported above.

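### For withdrawal and craving (MNWS, QSU-brief), the planned abstinence analysis estimates a total effect of product use plus abstinence; a contrast with the last on-product reading is needed to answer the protocol's question.

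*SAP*

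**What the plan says.** The protocol (Study 2, Abstinence Assessment Session) schedules one visit 18 to 30 hours after Week 12. Its purpose is to "determine whether the experimental cigarettes have reduced the effects of abstinence on these measures relative to the control conditions". Abstinence is verified by a fall in breath CO of at least 50% from the Week 12 value.

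For this visit SAP section 7.3.1 states: "At this visit, measures of craving and withdrawal will be completed". The model is the two-time-point model used for cigarettes per day (CPD), but with baseline and the abstinence visit as its time points, "rather than the baseline and Week 12 visits reported above". Neither document plans a contrast of the abstinence visit with an on-product visit.

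On collection, SAP section 6.1 gives the schedule as "even weeks for nicotine dependence, odd weeks for nicotine withdrawal". The protocol agrees. MNWS and QSU-brief appear in the list headed "Experimental Visits: Study Weeks 1, 3, 5, 7, 9, and 11", where the craving item reads "QSU brief – with reference to assigned cigarette". The even-week list, which covers Week 12, contains neither scale. At baseline they are given at Baseline 1 only, when women smoke their usual brand and have had no study product.

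Section 7.3.1 also says that withdrawal scores will be examined much as CPD is, and refers to section 6 for the time points of each outcome.

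**The concern.** An effect of abstinence is most directly a change from smoking the assigned cigarette to not smoking it. The planned comparison starts 12 weeks earlier, from usual-brand smoking before any assigned product. Whatever 12 weeks of VLNC cigarettes do to everyday craving and withdrawal enters the result together with whatever abstinence does.

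If VLNC use lowers everyday craving and abstinence then raises craving equally in both arms, the planned analysis still shows a difference favouring VLNC. That could be reported as a reduced effect of abstinence when abstinence acted no differently. The reverse can also occur: the protocol's background raises increased withdrawal on very low nicotine cigarettes as a possibility, and this could hide a real difference.

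A smaller gap lies beside it. The CPD model applied to withdrawal scores uses baseline and Week 12, but these scales have no Week 12 value and no substitute end point is named.

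**Working it through.** The plan states no figure to reproduce here. The check has two parts: which visits hold which measures, and what the planned contrast contains.

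**Visits (protocol Study 2 assessment lists; SAP section 6)**

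| Measure | On-product visits | Week 12 | Abstinence visit |
|---|---|---|---|
| MNWS, QSU-brief | Weeks 1, 3, 5, 7, 9, 11 | no | yes |
| CPT, assigned cigarette | Weeks 2, 6, 12 | yes | yes |
| BDI, OASIS | weekly | yes | yes |

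The collection gap is specific to MNWS and QSU-brief. The daily telephone system does not fill it, because it asks about withdrawal only in the weeks before and after randomisation. The nominal gap from Week 11 to the abstinence visit is 7 days + 1 day = 8 days.

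**Decomposition.** Let B be baseline, L the last on-product reading and A the abstinence visit. Since A - B = (L - B) + (A - L) in each arm, the between-arm difference is

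planned = [(L - B)VLNC - (L - B)UB] + [(A - L)VLNC - (A - L)UB] = product effect + differential abstinence effect.

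If VLNC lowers on-product craving by d relative to usual brand, and abstinence adds the same amount a in both arms, the planned contrast is (B - d + a - B) - (B + a - B) = -d. The abstinence contrast is a - a = 0.

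**Illustration.** The scores are assumed, not from the documents. Usual brand is 10 / 10 / 12 (B / L / A) throughout.

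| VLNC B / L / A | Planned | Product | Abstinence |
|---|---|---|---|
| 10 / 7 / 9 | (9-10)-(12-10) = -3 | (7-10)-(10-10) = -3 | (9-7)-(12-10) = 0 |
| 10 / 10 / 9 | -3 | (10-10)-0 = 0 | (9-10)-2 = -3 |
| 10 / 13 / 9 | -3 | (13-10)-0 = +3 | (9-13)-2 = -6 |

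One planned value fits all three patterns. A contrast using L tells them apart.

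**Reference cigarette.** Baseline 1 QSU-brief refers to the usual cigarette; the odd-week and abstinence-visit versions refer to the assigned one. In the VLNC arm the product asked about therefore changes between the two planned time points, while in the usual-brand arm it does not. An on-product reference removes this difference.

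**The case against.** The strongest reply is that the planned contrast is legitimate and the alternative is not plainly better. Randomisation makes baseline-to-abstinence a fair between-arm comparison of abstinent-state craving, and the protocol asks about effects relative to control. The on-product contrast has a mirror-image weakness, because the product can move its starting point. With usual brand at 10 / 10 / 12 as before:

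- VLNC 10 / 7 / 12 gives (12-7) - (12-10) = +3, an apparently worse abstinence effect although abstinent craving is the same in both arms.
- VLNC 10 / 13 / 13 gives (13-13) - (12-10) = -2, apparent protection only because scores were already raised on product.

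This stands. Neither contrast should be read alone, and ranking one above the other is partly preference.

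A second reply is that the on-product trajectory will be estimated anyway, since the analyses modelled on CPD include one with all time points, and section 7.3.1 points to section 6 for outcome-specific schedules. This stands in part. A reader would have most of the pieces, but no contrast of the abstinence visit with an on-product reading is prespecified, and subtracting estimates from separate models of the same women gives no valid standard error. The pointer to section 6 shows that schedules differ, but does not say which visit replaces Week 12.

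A reader might also infer that the trial's data cannot separate abstinence from product use. The documents do not support that: Week 11 MNWS and QSU-brief are collected on the assigned product. Nor does the gap extend to every measure at the session, since CPT, BDI and OASIS are collected at both Week 12 and the abstinence visit.

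**Conclusion.** The point holds for the analysis as specified. For MNWS and QSU-brief, the only planned abstinence analysis estimates the total effect of 12 weeks of assigned product plus abstinence, and does not by itself answer the protocol's question. The Week 12 model for withdrawal scores also lacks its end point.

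The size cannot be given in scale units. The contamination equals the on-product difference d, for which the documents give no value or range; the -d result assumes an equal abstinence effect in both arms. The range of 0 to -6 shows only that one planned value is compatible with quite different answers.

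The reach is limited. The primary endpoint is Week 12 CPD. The SAP lists withdrawal among additional measures, and the protocol lists MNWS and QSU-brief as secondary endpoints. CPD, the sample size and the primary conclusion do not change. It would be wrong to call the planned contrast invalid: it is a sound total effect that needs that label and a companion.

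**What to change.** In SAP section 7.3.1:

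1. For MNWS and QSU-brief, prespecify a condition-by-time contrast of the abstinence visit with the last on-product reading. That is Week 11 as now collected, or Week 12 if the two scales are added there for remaining participants.
2. For CPT, use Week 12 as the reference, since it is already collected.
3. Keep the baseline-to-abstinence contrast, label it a total effect, and report and interpret the two together. One model with baseline, on-product and abstinence time points would give both with consistent standard errors.
4. Name Week 11 as the end point of the withdrawal and craving model that now borrows the Week 12 wording.

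The cost with Week 11 is SAP wording, one extra contrast and an approximate reference about 8 days earlier; no new data are needed. Adding the scales at Week 12 means two short self-report forms at a visit already attended, but needs a protocol change at two sites and leaves a mix of Week 11 and Week 12 references. That mix should be stated, with Week 11 for all women shown as a check.

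One limit remains under either contrast. Women who miss the CO criterion do not complete MNWS or QSU-brief at the abstinence visit, so the analysed group is selected after randomisation. The report should say so and give the numbers by arm.

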#### **7.4. Secondary Endpoint Analysis**

Repeated measures analysis of variance will be used for the analysis of most secondary endpoints. Analyses will conform to the methods outlined above for primary endpoints. These outcomes include use of other nicotine products and biomarkers of exposure to tobacco carcinogens. Use of multiple nicotine products will be collected through the IVR system, as the response to questions asking whether the participant used smokeless tobacco, e-cigarettes or nicotine replacement products. Because responses are recorded as Yes/No, the responses will be aggregated on a weekly basis and are expressed as the number of days that other nicotine products are used.

Biomarkers will be analyzed on natural log scales so that ANOVA model

assumptions of normality and equal variances hold. Geometric means in original units will be calculated as well. Interaction terms between BMI and cigarette condition will be added to these models to explore possible moderating effects of obesity on the relationship between RNC cigarettes and biomarkers.

Differences between groups in self-reported quit and cigarette reduction rates at the 30 day post-intervention follow-up period will be evaluated using Chi-squared tests, as will be the case for other discrete outcomes such as drop-out rates. Secondary analyses using logistic regression will be completed to identify factors associated with cessation and retention. Candidate factors, in addition to condition, include subjective responses to the products, willingness to pay for the product (CPT), and withdrawal. SAS (SAS Institute Inc., USA) will be used for all analyses.

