At the end of the first baseline visit, participants will be trained to use the Interactive Voice Response (IVR) System, which will contact participants each day throughout the study and ask about their smoking behavior as well as withdrawal symptoms the week before and after randomization. We will also review the IVR adherence incentive program, which consists of \$1 per call plus a \$10 bonus for seven consecutive calls. Participants may be provided a study cell phone if they have unreliable telephone access, do not have enough monthly cell phone minutes or prefer not to use their own phone.

The IVR system is operated by TeleSage. To be enrolled in the IVR system, research staff will enter the participant's initials, telephone number, subject identifier, and visit dates into the IVR TCORS website. Identifying information (initials and telephone numbers) will not be extracted with the data by the bioinformatics group. Please refer to TeleSage's privacy statement and HIPAA compliance form for additional information.

Baseline 2 biological specimens:

- 1) Urine sample for smoking biomarker assessment:

Participants will be asked to provide a urine sample (first void of the day) at the second baseline session for biomarker assessment. Samples will be stored at temperatures no more than -80°C. The tobacco-specific carcinogen biomarkers are total NNAL and PAH. Total cotinine levels will also be assessed to measure daily nicotine exposure. Participants will be reminded with a phone call the day before the visit, those who forget will be asked to return to the lab with their first void

urine sample or staff can arrange to meet the participant off campus to pick up their urine sample.

Biomarker shipping and storage:

Biomarkers will be shipped quarterly to the University of Vermont Laboratory for Clinical Biochemistry Research ([name] Lab). The [name] Lab will serve as a central repository for all biomarker specimens and will be responsible for distributing specimens to the appropriate labs on a quarterly basis. Urine samples will be analyzed and stored at the University of Minnesota [name] Lab.

Study 2 Experimental Procedures

Experimental Period:

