## **7.6. Missing Data**

We will test the pattern of missing values using Little's MCAR test, and, assuming that the data are missing at random, we will employ statistical procedures that are based on maximum likelihood estimates, which will allow the inclusion of all subjects without imputation of missing values. The maximum likelihood approach estimates the parameter values that would maximize the probability of observing the data collected. In the event of missing variables, the likelihood for a given individual is the probability of observing the non-missing variables. Thus, the maximum likelihood approach allows the use of data from participants for the time period for which data is available, but not for time periods for which the data is missing. This procedure uses information from earlier time periods to estimate the effects of later time periods, while also accounting for the uncertainty of the projection in the computation of standard errors and test statistics. While maximum likelihood estimation is considered superior to imputation methods for the treatment of missing data in clinical trials, additional analyses will be conducted using several imputation methods to test the sensitivity of these results. Imputations methods will include, but not be limited to, last observation carried forward and multiple imputation with the Markov Chain Monte Carlo (MCMC) method carried out in PROC MI in SAS.

In the case of non-random missing data, we will conduct sensitivity analyses using

multiple imputation with the Markov Chain Monte Carlo (MCMC) method carried out in PROC MI in SAS. If missing data is associated with experimental condition, we will conduct multiple imputation for each experimental condition. At least 10 imputed data sets will be generated, with the experimental-condition effect being assessed in each imputed data set. A final single assessment of experimental condition differences will be obtained from combining the results across the imputed datasets using PROC MIANALYZE in SAS. The results of these analyses will be compared to the primary analysis to evaluate the robustness of our conclusions.

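### Other nicotine product use is a weekly count of Yes days with no denominator and no rule for missed IVR calls, so unequal call completion can create or hide a difference between conditions

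*SAP*

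**What the plan says.** SAP 7.4 names the source: "Use of multiple nicotine products will be collected through the IVR system". The questions cover smokeless tobacco, e-cigarettes and nicotine replacement. The answers are binary ("Because responses are recorded as Yes/No"), and the weekly outcome is defined from them as follows: "the responses will be aggregated on a weekly basis and are expressed as the number of days that other nicotine products are used".

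The method is set in the same section: "Repeated measures analysis of variance will be used for the analysis of most secondary endpoints". The outcome is named among those covered: "These outcomes include use of other nicotine products and biomarkers of exposure to tobacco carcinogens".

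SAP 7.6 treats missing data by time period. A participant contributes the periods for which she has data, "but not for time periods for which the data is missing". It does not mention missed days inside a week.

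The Protocol (Interactive Voice Response System) describes daily calls, paid at $1 each plus a $10 "bonus for seven consecutive calls". Its compliance review sessions include counselling on IVR completion. Its Outcome Variables list includes a timeline follow-back (TLFB) measure of other tobacco use, but the SAP names only the IVR for this outcome.

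**The concern.** A number of days per week is interpretable only if the number of days observed is known. Both documents are silent on that, so the plain reading is a sum of Yes answers. On that reading a woman who answers 4 of 7 calls can score at most 4. The SAP avoids the problem for cigarettes per day, where section 6.1 averages the daily reports, but not here.

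The outcome matters. The Protocol's background raises the possibility that women given very low nicotine content (VLNC) cigarettes will turn to other products to keep up their nicotine level, and regards this as especially worrying in pregnancy. Use of multiple nicotine products is part of Secondary Aim 1. If completion were lower on VLNC, a plain count would err towards reassurance; if it were lower on usual brand, it would err towards a false signal.

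**Working it through.** **No planned figure to reproduce.** The documents give no power, effect size, completion rate or use rate for this outcome. One related figure confirms the call schedule: 13 weeks x (7 x $1 + $10) = $221, the stated maximum for IVR reports. Seven calls a week are therefore expected over 13 weeks.

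**Inputs.** Let p be the share of days with use and r the share of calls answered. Both are assumed: p = 10%, 20% or 30%, and r from 50% to 100%. The top of the range for p matches the entry limit of 9 days in 30, since 9/30 x 7 = 2.1 days per week.

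**Step 1: the expected count.** If Yes answers are added and missed days are unrelated to use, the expected weekly count is 7 x p x r.

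| Use on days | All calls answered | 90% | 70% | 60% |
|---|---|---|---|---|
| 10% | 0.70 | 0.63 | 0.49 | 0.42 |
| 20% | 1.40 | 1.26 | 0.98 | 0.84 |
| 30% | 2.10 | 1.89 | 1.47 | 1.26 |

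**Step 2: effect on the comparison.**
- Equal completion: at 20% use and 90% answered in both conditions, each shows 1.26 instead of 1.40. Use is understated, but there is no false difference.
- A false difference: equal use of 20% with 90% v 70% answered gives 1.26 - 0.98 = 0.28 days per week.
- A hidden difference: true use of 2.1 v 1.4 days with 60% v 90% answered gives 7 x 0.3 x 0.6 = 1.26 and 7 x 0.2 x 0.9 = 1.26. This is a break-even case, picked to show that cancellation is possible; it is not a forecast.

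**Step 3: type I error.** I simulated one week with 45 women per condition and identical true use. Each woman's use probability came from a beta distribution with a + b = 0.5 at 10% use and 1.0 at 20% and 30%. Each case had 4,000 runs and a two-sided t test at 0.05. The scaled count is 7 x days used / days answered.

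| Use on days | Calls answered | Error, plain count | Error, scaled count | Mean difference, plain count |
|---|---|---|---|---|
| 10% | 90% v 90% | 4.3% | 4.4% | -0.01 |
| 10% | 90% v 70% | 5.9% | 4.4% | 0.13 |
| 10% | 90% v 50% | 13.6% | 5.1% | 0.28 |
| 20% | 90% v 90% | 5.1% | 5.5% | -0.01 |
| 20% | 90% v 70% | 10.9% | 5.2% | 0.28 |
| 20% | 90% v 50% | 35.1% | 5.2% | 0.56 |
| 30% | 90% v 90% | 4.9% | 5.0% | -0.01 |
| 30% | 90% v 70% | 15.0% | 5.0% | 0.42 |
| 30% | 90% v 50% | 56.2% | 4.7% | 0.83 |

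With all calls answered, both measures gave 4.7%, 4.8% and 5.5% at the three use rates. The mean difference on the scaled count was within about 0.01 days of zero throughout.

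**Step 4: does the missing-data section cover it?** The unit of analysis is the week. A week with four answers still yields a number. Unless a rule declares it missing, the likelihood method, last observation carried forward and multiple imputation in SAP 7.6 have nothing to act on. No such rule is given.

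**Limits.** The simulation covers one week in two groups, not the full repeated measures model, and missed days were generated independently of use.

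**The case against.** A reader might infer that the SAP scores every missed call as a day of no use. It does not say so. The text would also permit scaling the count or setting a partly answered week to missing, and SAP 7.6 leaves missing periods out instead of filling them with zero. That objection stands. What remains is that no rule is stated and that the literal count behaves as shown above.

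A reader might also infer that analysis of variance is invalid for a 0-7 count. The simulation does not support that: with equal completion the normal-theory test kept an error of 4% to 6%. The log transformation carried over from section 7.3.1 ("Natural log transformations will be performed as needed so that ANOVA model assumptions of normality and equal variances hold") is undefined at zero, which favours a binomial model, but this is the lesser point.

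Nothing in the documents indicates that VLNC women will answer fewer calls. The payments and counselling apply to both conditions and work against missed calls. They make large gaps less likely without guaranteeing equality: one condition changes product and the other does not.

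Urinary cotinine at Baseline 2 and Weeks 6 and 12 gives a check on nicotine exposure that does not depend on the IVR, so substitution would not be wholly invisible. It cannot identify the source of the nicotine, nor the days of use.

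**Conclusion.** The point holds as an unstated denominator for one secondary outcome. Read literally, the count falls in proportion to calls missed. It misleads the comparison only if completion differs between conditions. At 90% v 70% answered and 10% to 30% use, the false difference is about 0.13 to 0.42 days per week and the type I error about 6% to 15%. At 90% v 50% the error is 14% to 56%.

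These sizes rest on assumed completion and use rates and on missed days being unrelated to use. They show what could happen and do not predict what will. The primary endpoint is unaffected, because cigarettes per day is a mean of daily reports. This is a worthwhile, cheap improvement, not a flaw that threatens the trial.

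**What to change.** In SAP 7.4, replace the weekly number of days with days used out of days answered.

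- **Model.** Preferably a binomial mixed model with the terms the SAP already uses: condition, visit, condition-by-visit, and random effects for site and participant. A count model with log(days answered) as offset is an alternative. A menthol term is not needed for this purpose. Under the binomial model a week counts according to the days answered, and a week with none drops out, so no arbitrary minimum is needed.
- **Reporting.** Give IVR completion by condition and week, and show use as 7 x days used / days answered.
- **Sensitivity.** The denominator assumes that missed days are unrelated to use, given the model. If women skip calls on days when they use other products, the new measure is biased too. Repeat the analysis with missed days set first to no use and then to use, or over a stated range of use rates for missed days.
- **Gaps.** State whether TLFB data will fill missed days. If so, apply the same rule in both conditions.

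The cost is a few sentences in the SAP, a different SAS procedure and slightly more analysis work. It needs no new data and no change in procedures for participants. The rule should be fixed before the data are examined by condition.
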